Two parallel surveillance for clinical hepatitis and pregnancy detection will be conducted. All enrolled women in the study will be provided with an immunization card with identification numbers and with a phone number to call if they become ill with jaundice or missed periods (>2 weeks from the expected start date) between the weekly home visits by the study field workers. The phone number will be answered by a study staff member who will make household visits to screen for suspected hepatitis, regardless of whether or not the woman is pregnant. Jaundice is recognized by lay language as “*Jaundeesh*” in the study area. More than 80% of households have access to a cell phone. Regular SMS messages will be sent to remind participants to report cases of jaundice. All women whose pregnancies are detected through the weekly home visits by the study field workers or routine MCH-FP visits will be visited every 2 weeks to collect information about pregnancy outcomes and to screen for clinical hepatitis. Laboratory diagnosis will be undertaken in both types of surveillance for any woman with acute onset of jaundice of any duration or with illnesses lasting for at least 3 days with at least three of the following symptoms: fatigue, loss of appetite, abdominal discomfort, abdominal pain in the right upper quadrant, nausea or vomiting (Shrestha, 2007, Clayson 1995). Suspected cases will be referred to Matlab hospital for clinical and laboratory examination. Surveillance for hepatitis will continue for approximately 2 years after the completion of all vaccinations.

Acute hepatitis cases with negative HEV diagnostics will be further investigated for other possible causes (other hepatitis such as hepatitis B).

Piloting of HEV Surveillance

We want to establish a surveillance system for detection of HEV disease through identifying hepatitis E virus (HEV) disease among patients with Hepatitis in adult female aged 16- 39 years before starting the main phase of the study.

Vaccine immune responses

A blood sample will be taken from all participants at baseline and one month after the last dose of the vaccine. Paired specimens from each individual will be tested together. Seroconversion will be determined using ELISA method (Zhu et al, 2010) and the rates will be compared between recipients of HEV vaccine and HBV vaccine. Serological immune correlates of protection will be determined by two methods: 1) comparing post-HEV vaccination titres in recipients of a complete regimen of HEV vaccine who develop HEV disease versus recipients who do not 2) the method which estimates protective level of antibodies by comparing the relative risk of the disease outcome using the reverse cumulative distribution curves of antibody responses in vaccinees and comparison group participants (Klugman 1996).

Titers of serum IgG anti-HEV antibodies, as well as of different isotypes for IgG (G1-G4) of these antibodies will be determined (following Wantai kit guidelines, China) at the different time points (baseline day 0, 1 month after dose 3 and at 2 years (24 to 35 months) after dose 3 or who received 1 or 2 doses).

Evaluation of specimen types for acute hepatitis cases

The feasibility of using dried blood spots (DBS) for detection of HEV RNA and HEV antibodies will be evaluated (Lee CE et al, 2011; Mohamed S et al, 2013) taking into account storage conditions (time and temperature) and sensitivity. EDTA-plasma, capillary blood on DBS and saliva samples (approx 2 ml) from 50 participants with established active HEV infection and 50 vaccinated participants will be collected for this project. Standard HEV ELISA anti-HEV IgM/IgG and PCR will be optimised and evaluated for the different types of material using plasma samples as gold standard.

Evaluation of risk factors and the natural course of HEV disease

A blood and stool sample will be collected from jaundiced patients. If HEV disease is confirmed by the presence of anti HEV IgM or HEV RNA, blood samples will be analysed for relevant biochemical, microbiological and immunological markers. This include viral load, HEV subtypes, other hepatitis infections, antibody titer, cellular response, cytokines, alanine transaminase (ALT), INR and albumin.. The patients symptoms and signs will be recorded regularly during the disease by health workers.

The following possible risk factors for severity of the disease will be looked for: Occupation, age, height, weight, body mass index, sanitation system, water use pattern, Anti-HEV IgG antibody level, immunological factors, viral load and viral sequence.

Pregnant women will be interviewed for other information (any complications during previous pregnancies, foetal loss etc.).

Incidence of HEV during pregnancy: All with confirmed symptomatic and asymptomatic HEV disease during pregnancy, matched with possible risk factors.

Mortality and morbidity of HEV disease during pregnancy: Natural course, clinical outcome and laboratory results of HEV disease during pregnancy will be recorded.

Pregnancy outcome in HEV infected pregnant women : Data on pregnancy outcome, including complications during delivery and health status of mother and child, will be collected on all participants and analysed together with records of eventual HEV disease and type, time and number of vaccine doses.

Economic analysis

Cost-effectiveness analysis (CEA) and cost-benefit analyses (CBA) will be carried out for HEV vaccine delivery to women in this setting taking the societal perspective (Cartwright, 2005). The cost of vaccination will thus be estimated and compared with its outcomes in terms of health gain (DALYs averted/QALYs gained) and economic gain (cost-saved from the society) (Manca et al. 2015; Murray and Lopez, 2013). Cost of vaccination (total cost, cost per vaccinated woman, marginal cost for vaccination) will be calculated for applying in both CEA and CBA. Costing of any intervention is concerned about systematic collection of information about resources used, categorizing the resources and analysing their costs (Drummond et al. 2005). Ingredient and budgetary approach will be utilized for this costing exercise considering the program perspective. All inputs, for instance, staff time, use of space, medical equipment, shared administrative costs, will be identified by visiting the site, interviewing the relevant key personnel and reviewing the documents of the vaccination program. Identified inputs will then be classified into capital and recurrent items as well as into fixed and variable items. Annuity of capital items (like, medical equipment, computer) will be done using the lifetime of such items for estimating their annual equivalent costs. In order to adjusting for the differential in timing of resources used, discounting rate of 3% will be applied for base analysis and 0% and 5% for sensitivity analysis. Cost per vaccinated will be calculated by dividing the total costs with the total number of vaccinated women.

Feasibility and acceptability of the vaccine

Operational feasibility of introduction of HEV vaccine will be assessed by in-depth interviews with health workers (15-20) (who will motivate women to bring to the health centre for vaccination) and health care providers (15-20) (providing vaccines to the study women). These interviews will help to identify operational barriers in motivating women for vaccination and in the storage and administration of vaccines. Acceptability of the vaccine will be assessed by conducting in-depth interviews with vaccine acceptors and non-acceptors. A total of 30-40 interviews will be conducted - half of which will be conducted with acceptors and the rest will be conducted with the non-acceptors.

Organization of the study

Study coordination

NIPH

The team at NIPH consist of [name], [name], [name], [name]. In addition, three researchers financed by funds from the Norwegian Research Council will be assigned to the project; [name] [name], [name] and [name]. NIPH will constitute a steering committee including representatives from the research partners, and will be chaired by Specialist Director Vaccines [name], PhD of the Norwegian Institute of Public Health (NIPH).

icddr,b

The team at icddr,b will be headed by [name] supported by other investigators. icddr,b will implement the study in collaboration with NIPH.

Sykehuset Innlandet

[name] will be collaborating researcher from this site.

ideSHi

[name] of ideSHi will be collaborating researcher from this site.

Study timeline

The overall timeline for the study and milestones are shown in table :

Activities	2016			2017			2018			2019		
Regulatory approvals/site preparation and training												
MoU/contract between NIPH, icddr,b, Innovax and Incepta												
Pretesting, Enrollment/vaccination of participants												
Pregnancy follow up, HEV surveillance												
Data collection and Lab analyses												
Data analysis, dissemination, report and manuscript writing												

Capacity building and technology transfer in Bangladesh

An important additional component of the proposed project will be the establishment of technology transfer of the vaccine from Innovax to a highly qualified Bangladesh vaccine producer, Incepta, for production of low-cost vaccine in Bangladesh for government immunization programmes. There is already established contact between these two producers. Incepta will receive bulk vaccine for the trial from Innovax and will package both the HEV and control (hepatitis B) vaccines in identical presentations. The agreement on technology transfer for fill finish and production in Bangladesh is in process.

Data Analysis

Describe plans for data analysis, including stratification by sex, gender and diversity. Indicate whether data will be analysed by the investigators themselves or by other professionals. Specify what statistical software packages will be used and if the study is blinded, when the code will be opened. For clinical trials, indicate if interim data analysis will be required to determine further course of the study.

Statistical methods and data analysis

Statistical Analysis

We will measure total vaccine protection as our primary objective in a per protocol analysis of three-dose vaccine recipients, using analytic methods to adjust for the design effect of cluster randomization (Halloran, 1997; Donner 2000). In this analysis we will compare the incidence of confirmed HEV disease in pregnant women who have been recipients of a complete three dose regimen of HEV vaccine or HBV vaccine and in whom the HEV disease episode begins at least 14 days after the third dose of vaccine. We will attempt to assess the indirect vaccine protection (defined as protection of non-HEV vaccinees in HEV vaccine clusters) and overall vaccine protection (defined as protection of all members of HEV vaccine clusters relative to all members of HBV vaccine clusters), but are aware that our trial may not be adequately powered for these analyses. Adverse events, immune responses to vaccines, and other outcomes will employ tests appropriate for comparison of categorical and dimensional outcomes, adjusted for the design effect of cluster randomization. All statistical tests will be evaluated at $P < 0.05$, two tailed.

In one main analysis (**Analysis 1**), we will compare waning of serum titers of IgG anti-HEV antibodies elicited by the third dose of HEV, measured 2 years (24 to 35 months) later after dose 3, among those who are 1) HEV seronegative at baseline and received HEV vaccine, 2) those who were HEV seropositive at baseline and received HEV vaccine, 3) who were HEV seropositive at baseline and received HBV vaccine, 4) participants who are HEV seronegative at baseline and received HBV vaccine (pure control group).

In a second main analysis (**Analysis 2**), we will also compare the decline in the attributable percentage of HEV seropositive (% HEV vaccinees who are IgG HEV serum antibody seropositive minus % of HBV vaccinees who are HEV seropositive) among those who are HEV seronegative at baseline until two years after the third dose. In secondary analyses we will conduct similar analyses of serum IgG subclass anti-HEV antibodies, as well as similar analyses among persons who only received only the first dose, or only the second dose of either vaccine or two doses due to receipt of incomplete vaccine regimens.

For cost-effectiveness analysis, cost per DALY averted and QALYs gained will be compared with Gross-Domestic Product per capita threshold for classifying the intervention into very cost-effective, cost-effective and not cost-effective. The vaccination program will be very cost-effective, cost-effective or not cost-effective if the cost-effectiveness ratio estimate is 1, 2 and 3 times less than the GDP per capita of the reporting country cost-effectiveness ratio (WHO 2003).

For cost-benefit analysis, the monetary benefits will be calculated by estimated costs saved (corresponding to cost of illness) due to HEV infection aversion through vaccination. Net benefit (total benefits minus total vaccination cost) and benefit-cost ratio (BCR) will be calculated, where positive value of net benefit and value more than 1 of BCR will indicate the acceptability of the vaccination against HEV.

The cost analysis will give the opportunity for modelling the costs for scaling up the vaccination program on the national level.

Data Safety Monitoring Plan (DSMP)

All clinical investigations (research protocols testing biomedical and/or behavioural intervention(s)) should include the Data and Safety Monitoring Plan (DSMP). The purpose of DSMP is to provide a framework for appropriate oversight and monitoring of the conduct of clinical trials to ensure the safety of participants and the validity and integrity of the data. It involves involvement of all investigators in periodic assessments of data quality and timeliness, participant recruitment, accrual and retention, participant risk versus benefit, performance of trial sites, and other factors that can affect study outcome.

Data Safety and Monitoring

A Data Monitoring Board (DSMB) will be tasked with monitoring the conduct of the trial, review the accumulating trial data and in particular reports of SAEs (related and not related, irrespective of severity) and make recommendations as appropriate. The study will be discontinued according to a priori defined stopping rules.

Ethical Assurance for Protection of Human rights

Describe the justifications for conducting this research in human participants. If the study needs observations on sick individuals, provide sufficient reasons for using them. Indicate how participants' rights will be protected, and if there would be benefit or risk to each participants of the study. Discuss the ethical issues related to biomedical and social research for employing special procedures, such as invasive procedures in sick children, use of isotopes or any other hazardous materials, or social questionnaires relating to individual privacy. Discuss procedures safeguarding participants from injuries resulting from study procedures and/or interventions, whether physical, financial or social in nature. [Please see Guidelines]

The study will be conducted in accordance with all applicable regulatory requirements.

The study will be conducted in accordance with the ICH Guideline for Good Clinical Practice (GCP), all applicable subject privacy requirements and the guiding principles of the Declaration of Helsinki. The study has been designed and will be conducted in accordance with the ICH Harmonized Tripartite Guideline for clinical investigation of medicinal products in the paediatric population (ICH E11) and all other applicable ethical guidelines.

Conduct of the study includes, but is not limited to, the following:

Institutional Review Board (IRB)/Independent Ethics Committee (IEC) review and approval of study protocol and any subsequent amendments and participants informed consent.

Use of Animals

Describe if and the type and species of animals to be used in the study. Justify with reasons the use of particular animal species in the research and the compliance of the animal ethical guidelines for conducting the proposed procedures.

Not Applicable

Collaborative Arrangements

Describe if this study involves any scientific, administrative, fiscal, or programmatic arrangements with other national or international organizations or individuals. Indicate the nature and extent of collaboration and include a letter of agreement between the applicant or his/her organization and the collaborating organization.

The Norwegian Institute of Public Health (NIPH) is a driving force in improving the health, quality of life and legal protection of the population. NIPH a wide range of internationally recognized scientific expertise reflected in participation in 26 projects in FP7 and an ERC grant in 2013. The NIPH also collaborates with the WHO, EU, EEA, sister institutions, universities, organizations and health authorities in low and middle income countries on global health issues. The NIPH is currently involved in several vaccine-trials abroad and nationally, including Ebola vaccine in Guinea, meningococcal vaccine in Ethiopia and rotavirus vaccine in India and Norway.

Incepta Pharmaceuticals- Established in 1999, one of the largest pharmaceutical industry is involved in producing vaccine and drugs.

Xiamen University and Inovax Biotech in China developed HEV 239 (Hecolin™) vaccine.

ideSHi- Optimization and validation of DBS ELISA will be performed from samples of HEV patient's serum those are being collected for completion of PhD Project of [name], who is working at our collaborating institute ideSHi. These optimization and validation of the assay will be performed in both places and is very much needed for understanding and assay of samples of vaccine participants from HEV pilot project. Optimization and validation of the DBS ELISA assay will help to conduct a large scale study to see the vaccine efficacy and thus help to prevent maternal and perinatal mortality.

Facilities Available

Describe the availability of physical facilities at site of conduction of the study. If applicable, describe the use of Biosafety Level 2 and/or 3 laboratory facilities. For clinical and laboratory-based studies, indicate the provision of hospital and other types of adequate participant care and laboratory support services. Identify the laboratory facilities and major equipment that will be required for the study. For field studies, describe the field area including its size, population, and means of communications plus field management plans specifying gender considerations for community and for research team members.

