The vaccine has been shown to be safe and highly efficacious against HEV disease in a large phase III trial in China with over 100,000 participants (100% after 3 doses of vaccine, 95% CI: 72.1-100.0), where it is commercially manufactured and licensed sale (Zhu, 2010). The majority of cases in this trial were due to genotype 4, indicating that the vaccine was able to confer genotype-heterologous protection. The vaccine was highly immunogenic with seroconversion rates of 98-100% among vaccinees (Zhang, 2014). The study did not provide sufficient data (not powered) to show efficacy in preventing HEV disease during pregnancy. Pregnant women are most vulnerable to HEV-infection and have the greatest impact of an effective vaccine.

Summary of known and potential risks

In phase 1, 2 and a large phase 3 study conducted by the manufacturer, preclinical toxicity of HEV239 was assessed and Hecolin was well tolerated and safe for use in healthy adults. AEs were mainly local with pain, swelling and itching at the injection site. The rate of AEs was similar in the study groups and the placebo groups (receiving a Hepatitis B vaccine). AEs of grade 3 or more were reported only very rarely, and include injection site swelling, fever and headache.

An extended follow-up study from the phase 3 study collecting data on safety for up to 4.5 years after the first vaccine dose, showed the number of reported SAEs (4792 vs 4667; $p=0.179$) and the number of participants with one or more SAE (4602 vs 4490; $p=0.221$) to be comparable between the vaccine and placebo groups. None of the SAEs was judged by the principal investigator (who reminded masked to treatment assignment) to be related or possibly related to the hepatitis E vaccine (Zhang, 2015).

Phase III retrospective cohort study - pregnant women

There are limited data on safety of Hecolin® on maternal and fetal outcomes following use during pregnancy.

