Pretesting Before proceeding a large scale trial, we will perform pretesting of the study. We will look mainly at/on the safety and also immunogenicity of this vaccine with this small sample size. This will be done outside of the MCH-FP area but within the HDSS area. The sample size for the pretesting phase will be 25 female and 25 male from the HEV and HBV group respectively (estimated assuming 70% seroresponse in vaccine group vs. 10% in control, $p < 0.05$, 2 tailed, 0.9 power). The sample will be randomly selected among nonpregnant women aged 16-39 years and male will be randomly selected from the age group of 16-39 years. We will observe each participant for 30 minutes after each vaccination. After each dose field worker will visit daily for 7 days at their homes enquiring about any untoward events. Blood will be collected before vaccination and 1 month after the second dose. Process for determining immunogenicity will be same as described in the protocol.

We want to find out the strength and longevity of the immune reaction to a two-dose schedule compared to the standard three-dose schedule of the vaccine for the pilot study. We will collect one blood sample

(maximum 3ml) from all participants of pilot study (100) to determine the immune response and an additional 9 ml blood from the 10 persons previously selected to assess the cellular response approximately 2 years after first vaccination.

To better understand the persistence of immunological responses 2 years (24 to 35 months) after the last dose of the vaccine we will do a sub-study under this main study. We will sequentially enrol for this add-on study from the list of original enrollment and identify eligible participants who received 3 doses of vaccine and completed follow up 2 years (24 to 35 months) and also who received 1 or 2 doses of vaccine (incomplete schedule). We will include total 1,760 (440 participants in each group) HEV vaccine study participants for this sub-study among those who are 1) HEV seronegative at baseline and received HEV vaccine, 2) those who were HEV seropositive at baseline and received HEV vaccine, 3) who were HEV seropositive at baseline and received HBV vaccine, 4) participants who are HEV seronegative at baseline and received HBV vaccine (pure control group).

Enrolment

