After each vaccination dose, the participant will be observed for 30 minutes and a field worker will visit daily for 7 consecutive days at their homes enquiring about any untoward events. They will also be asked to report if they have any local reactions (i.e., erythema, swelling, induration and pain at the injection site), systemic reactions (i.e., nausea, malaise, myalgia, arthralgia, headache) and fever within 7 days after vaccination.

Procedures for the vaccination visit, including recording immediate post vaccination adverse events, are described in SOP “Post Vaccination Observation” Procedure and SOP “Immediate Post Vaccination Reaction Management Procedure”.

Post vaccination scheduled visits

All participants will have a blood sample taken one month after the last dose of the vaccine. All women whose pregnancies are detected through the weekly home visits by the study field workers or routine MCH-FP visits will be visited every 2 weeks to collect information about pregnancy outcomes and to screen for clinical hepatitis.

Close of study visits in the pregnant cohort.

The last study visit to pregnant women included will be 14 days after birth. The participant’s general health status will be recorded and information on any changes in the participant’s occupation, residence or other important time-varying factors will be collected at this visit. Information on pregnancy outcome and health status of the child will be recorded. Participants will be advised there will be no further scheduled study visits but that they should inform the study team by telephone of any possible serious adverse events or signs of hepatitis.

Close of call

The detection for pregnancies and hepatitis surveillance will end atleast 2 years after the last dose of vaccination is given.

Criteria for Participant Discontinuation

Participants may be discontinued from study treatment and assessments at any time. Specific reasons for discontinuing a participant for this study are:

- Voluntary discontinuation by the participant who is at any time free to discontinue his/her participation in the study, without prejudice to further treatment.
- Safety reason as judged by the Principal Investigator
- Major protocol deviation
- Incorrect enrolment ie, the participant does not meet the required inclusion/exclusion criteria for the study
- Participant lost to follow-up

Procedures for Discontinuation

Participant Discontinuation

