Participant will be offered a clinical assessment for safety prior to leaving the study, consistent with the assessments done during follow-up visits. Furthermore, SAEs will be cared for and followed through until a cause has been established, even if the participant is withdrawn from the study.

Trial Discontinuation

The whole trial may be discontinued at the discretion of the PI or the sponsor in the event of any of the following:

- Occurrence of AEs unknown to date in respect of their nature, severity and duration
- Medical or ethical reasons affecting the continued performance of the trial
- Difficulties in the recruitment of participants
- Cancellation of drug production

The sponsor and principal investigator will inform all investigators, the relevant Competent Authorities and Ethics Committees of the termination of the trial along with the reasons for such action. If the study is terminated early on grounds of safety, the Competent Authorities and Ethics Committees will be informed within 15 days.

Safety Monitoring and reporting

The investigator is responsible for the detection and documentation of events meeting the criteria and definition of an adverse event (AE) or serious adverse event (SAE). Each participant will be instructed to contact the investigator immediately should they manifest any signs or symptoms they perceive as serious.

The methods for collection of safety data are described below.

Definitions

Adverse Event (AE)

An AE is any untoward medical occurrence in a participant administered a pharmaceutical product and which does not necessarily have a causal relationship with this treatment.

An adverse event (AE) can therefore be any unfavourable and unintended sign (including an abnormal laboratory finding), symptom, or disease temporally associated with the use of a medicinal (investigational) product, whether or not related to the medicinal (investigational) product.

The term AE is used to include both serious and non-serious AEs.

If an abnormal laboratory value/vital sign are associated with clinical signs and symptoms, the sign/symptom should be reported as an AE and the associated laboratory result/vital sign should be considered additional information that must be collected on the relevant CRF.

Serious Adverse Event (SAE)

Any untoward medical occurrence that:

- Results in death

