The definition of a routine clinical procedure is a procedure, which may take place during the study period and should not interfere with the study vaccine administration or any of the on-going protocol specific procedures. If anything untoward occurs during an elective procedure and satisfies any of the criteria for SAE, this will be documented and reported.

Time Period for Reporting AE and SAE

For each participant the standard time period for collecting and recording AE and SAEs will begin at the time of the first vaccination and will continue for at least 1 year following the last dose of study treatment for each participant.

During the course of the study all AEs and SAEs will be followed up actively and passively for each participant; events will be followed up to resolution, unless the event is considered by the investigator to

be unlikely to resolve due to underlying disease. Every effort will be made to obtain a resolution for all events, even if the events continue after study completion.

Recording of Adverse Events

If the participant has experienced adverse event(s), the investigator will record the following information in the CRF:

- The nature of the event(s) will be described by the investigator in precise standard medical terminology (i.e. not necessarily the exact words used by the participant).
- The duration of the event will be described in terms of event onset date and event ended data.
- The intensity of the adverse event: Mild/ Moderate / Severe; according to Common Terminology Criteria for Adverse Events version 4.0 (CTCAE).
- The Investigator will assess the causality of all SAEs, using the following question: “Is there a reasonable possibility that the SAE may have been caused by the study vaccine?” After assessment of causality, the investigator will classify the SAE as defined below:

Unrelated:

There is not a temporal relationship to investigational product administration (too early, or late, or investigational product not taken), or there is a reasonable causal relationship between non-investigational product, concurrent disease, or circumstance and the AE.

Unlikely:

There is a temporal relationship to investigational product administration, but there is not a reasonable causal relationship between the investigational product and the AE.

Possible:

There is reasonable causal relationship between the investigational product and the AE. Dechallenge information is lacking or unclear.

Probable:

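### The named local reactions to report after vaccination omit injection-site itching, which the plan lists among the three main known reactions, so itching may be recorded less completely than pain and swelling

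*Combined protocol and SAP*

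**What the plan says.** **Known reactions.** Under Summary of known and potential risks, the combined protocol and SAP reports from the manufacturer's studies that "AEs were mainly local with pain, swelling and itching at the injection site".

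**What women are asked in this trial.** Under Visits to participants, Eligibility and vaccination visits, two things happen after each dose. First, "a field worker will visit daily for 7 consecutive days at their homes enquiring about any untoward events". Second, women are in addition asked to report "local reactions (i.e., erythema, swelling, induration and pain at the injection site", together with "systemic reactions (i.e., nausea, malaise, myalgia, arthralgia, headache) and fever within 7 days after vaccination". Both lists are introduced by i.e., so they read as complete, and neither has an entry for other reactions.

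**Pretesting.** The Pretesting section repeats the open enquiry ("After each dose field worker will visit daily for 7 days at their homes enquiring about any untoward events") and names no individual reactions.

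**Definition and follow-up.** The safety definitions state that "An AE is any untoward medical occurrence in a participant administered a pharmaceutical product", and under Time Period for Reporting AE and SAE, "all AEs and SAEs will be followed up actively and passively for each participant".

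**Analysis.** Safety is a secondary objective. The Secondary endpoints section describes it in terms of serious adverse events, but the Statistical Analysis section also covers non-serious events: "Adverse events, immune responses to vaccines, and other outcomes will employ tests appropriate for comparison of categorical and dimensional outcomes", adjusted for clustering. No rate is defined for any single local reaction.

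**The concern.** The plan identifies three main local reactions to the study vaccine. Two of them, pain and swelling, are on the list that women are asked about by name. The third, itching, is on neither the local nor the systemic list, and no reason is given.

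A symptom that is named to the respondent and one that must be recalled under a general question are not collected in the same way. If the general question picks up fewer episodes, the itching rate will be too low when read beside pain and swelling, and the absolute difference between the hepatitis E and hepatitis B vaccine arms will be too small. Mild itching would not normally qualify as a serious adverse event, so ordinary adverse event recording is the only place where it would appear. The local-reaction contrast is of some interest here because the two products differ in injected volume (0.6 ml against 0.5 ml or 1 ml by age, under Allocation of intervention and control).

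**Working it through.** The documents give no itching rate and no figure for how completely an open question captures it. There is no stated number to reproduce, so the check is a comparison of the text, followed by the algebra of what unequal capture would do.

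**Step 1. Set the lists side by side.**

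| Reaction | Named as a main known local reaction | Named in the 7-day local list | Covered by the open daily question |
|---|---|---|---|
| Pain | yes | yes | yes |
| Swelling | yes | yes | yes |
| Itching | yes | no | yes |
| Erythema | no | yes | yes |
| Induration | no | yes | yes |

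The systemic list (nausea, malaise, myalgia, arthralgia, headache, plus fever) does not contain itching either. Of the three main known reactions, two have both routes of capture and one has only the open route.

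**Step 2. Is itching actively sought at all?** Yes, in general terms. The daily visit asks about any untoward event, the adverse event definition is broad enough to include itching, and follow-up is described as active as well as passive. The gap is the missing name, not a missing enquiry.

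**Step 3. Effect of incomplete capture.** Let p1 and p0 be the true itching risks in the hepatitis E and hepatitis B arms, and s the share of episodes captured by the open question, with s between 0 and 1 and the same in both arms.

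- Observed risks: s × p1 and s × p0.
- Observed risk difference: s × p1 − s × p0 = s × (p1 − p0), which is smaller by the factor s.
- Observed risk ratio: (s × p1) / (s × p0) = p1 / p0, which is unchanged.
- Precision: for uncommon events the standard error of the log risk ratio is roughly √(1/a + 1/b), with a and b the event counts in the two arms. Both counts fall by the factor s, so the standard error rises by about 1/√s.

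If s = 1 nothing is lost. The documents do not allow s to be estimated.

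**Step 4. Could capture differ by arm?** If the shares were s1 and s0, the observed ratio would be (s1/s0) × p1/p0. Nothing in the documents points to s1 ≠ s0. The trial is described as double-blind, and those who vaccinate take no part in follow-up or adverse event assessment.

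**The case against.** The strongest answer is that itching is already covered. A field worker asks about untoward events on seven consecutive days after each of three doses, and itching is plainly an untoward event. This stands, and it rules out a reading that a reader might otherwise take from the list alone, namely that itching is recorded only when a woman volunteers it.

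Several further points also stand:

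- The text does not say that the named list is read out at every daily visit. It could be an instruction to women about what to report. Either way, pain and swelling are named to them and itching is not.
- The 7-day form and the post-vaccination procedures are not part of the documents. The form may already have an itching field, in which case only the protocol text needs aligning.
- The safety endpoint is described through serious adverse events. The reactions of grade 3 or more named in the known-risks summary (injection-site swelling, fever, headache) are all on the lists. Efficacy and the detection of serious events are unaffected.
- The General Study Design section refers to an ongoing study with blood already collected, and the Pretesting section describes a sample about two years after first vaccination. Vaccination may be over, so a change to the form could come too late.

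What the objection does not remove is the asymmetry. The plan itself adds the named list to the open question. It does so for two of the three main known reactions and gives no reason for leaving out the third.

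**Conclusion.** The point holds as a minor one. The named list omits a reaction that the plan itself counts among the three main ones, so itching is collected by a weaker route than pain and swelling and may be under-recorded relative to them. The size cannot be derived from the documents and could be zero. If the loss is equal in the two arms, absolute rates and the risk difference shrink, while the risk ratio stays unbiased but less precise.

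Two stronger conclusions should not be drawn. A reader might infer that the itching rate is understated as a matter of fact; the documents contain no capture figure that would show this. A reader might also infer that the rate would not be comparable with the earlier large trial; the documents do not say how that trial collected itching.

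The verdict assumes that the lists introduced by i.e. are meant to be complete and that the form follows the protocol text.

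**What to change.** Under Eligibility and vaccination visits, add itching at the injection site to the named local reactions. Add it to the 7-day post-vaccination form if it is not already there. In the adverse event analysis, tabulate it by arm with the other local reactions, with the same adjustment for clustering. If the omission was deliberate, state why.

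If vaccination is already complete, leave the data as they are, report itching as an unprompted event, and do not set its rate directly against those of the prompted reactions.

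The cost is one item on an enquiry already made at existing visits, or one sentence in the analysis plan if collection has ended. No dose, schedule or clinical rule is affected.
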